## 8.5 Primary Analysis

Safety analyses will be performed for all patients who enroll in the study. The study will use the NIH Division of AIDS Table of Grading of Severity of Adult and Pediatric Adverse Events V2.0 to

classify adverse events. Descriptive statistics (percentages) will be reported for the incidence of any Adverse Events reported, including suicidality as measured by the C-SSRS. Median scores will also be calculated for total scores of the feasibility measures: CSS, CrEQ, and PEQ-S. The differences of mean pre- and post-treatment scores on the CORF will be calculated. Differences in individual pre- and post-treatment MoCA scores will be assessed for each individual. Therapist protocol adherence will be reported as a rate of discussion topic deviations from the protocol.

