
Rationale for Study (continued)	
as prior trials [24], but the psychotherapy sessions will employ a modified form of Supportive-Expressive Group Therapy (SEGT) [25]. SEGT is a widely used, manualized, evidence-based group intervention for existential distress in patients with life-threatening disease [26]. The current study will be the first modern study of psilocybin-assisted group psychotherapy.
 
In the current study, the group psychotherapy format functions as a standardized context in which patients' experiences of social support can be objectively observed pre- and post-psilocybin. This is helpful because while prior trials of psilocybin-assisted psychotherapy evaluated clinical outcomes, they did not make use of validated measures of psychotherapeutic process. By administering psilocybin as an adjunct to SEGT, we will be able to explore quantitatively and qualitatively not only the intrapersonal, but also the interpersonal, therapeutic mechanisms catalyzed by psilocybin in LTAS suffering from demoralization.

Primary Objective	To demonstrate the safety and feasibility of Psilocybin-Assisted Supportive-Expressive Group Therapy (PA-SEGT) for demoralization in LTAS.
Exploratory Objectives	
To explore the preliminary efficacy of PA-SEGT for improving demoralization, complicated grief, depression, anxiety, quality of life, functional social support, post-traumatic growth, openness to experience, mindfulness, social connection, nature relatedness and ART medication adherence in LTAS.
 
To explore quantitatively and qualitatively the mechanisms through which PA-SEGT addresses existential distress in LTAS.

Study Design	Open-label mixed-methods pilot study of individual oral psilocybin drug sessions (with escalating dose) combined with an evidence-based, manualized brief group psychotherapy.
Number of patients	36 (maximum, with a minimum of 8)
Duration of Therapy	8 weeks after the initiation of the intervention.
Duration of Follow up	3 months after completion of the intervention.
Duration of study	2 years from the time the study opens to accrual.
Study Therapy	Psilocybin (4-phosphoryloxy-N,N-dimethyltryptamine) will be administered once at a moderate-to-high dose of 0.3mg/kg (or 0.36mg/kg) po during an individual medication visit to be held after 4 group therapy visits have been completed. Patients will undergo a total of 10 group psychotherapy sessions.

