## 1.4 Study Hypotheses

### Primary

1. The study will recruit, consent and enroll at least 18 subjects (in 3 groups of 6 members) over 18 months; these subjects will complete all treatment and evaluation sessions and they will experience no treatment-emergent serious adverse events.

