## 2 Objectives of the Study

### 2.1 Objectives

#### 2.1.1 Primary Objective

- To demonstrate the safety and feasibility of Psilocybin-Assisted Supportive-Expressive Group Psychotherapy (PA-SEGT) for demoralization in long-term AIDS survivors (LTAS).

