### **8.2 Determination of Sample Size and Accrual Rate**

#### **8.2.1 Sample Size and Power Estimate**

This pilot study of the safety and feasibility of psilocybin-assisted group therapy aims to enroll at least 18 subjects, and will have a maximum total sample size of 36. We estimate needing to enroll 18 subjects given attrition rates of up to 45% reported in trials of other group therapies for existential distress in palliative care patients [114]. For comparison, four different safety and feasibility pilot studies of psilocybin-assisted psychotherapy have been conducted over the last two decades, and have included 9, 10, 12 and 15 patients each [18, 107, 108, 110]. Four recently published feasibility pilot studies of meaning-focused group psychotherapies for palliative care patients have included 5, 11, 11, and 16 patients each [40, 178-180].

Group therapy studies should include at least 2 groups of at least 4-6 members [135], so we plan to have at least 8 subjects complete the intervention. We expect to be able to enroll at least 6 subjects every 6 months.

Because the proposed study is a pilot focused on investigating safety and feasibility, power calculations for efficacy measures are not indicated. Pilot studies are often used to estimate values that are then utilized in power calculations for full-scale trials. Indeed, we will estimate effect size (ES) and the intraclass correlation coefficient (ICC) [132] for the intervention based on our preliminary efficacy results. Group psychotherapy trials generally require large sample sizes to demonstrate statistical significance in change in efficacy measures given the likely interdependence of clinical outcomes when interventions are delivered in groups [132, 133]. Thus, future full-scale trials can utilize our estimates to derive adequate, and likely large, sample sizes.

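### The primary objective is to demonstrate safety, but section 8.5 reports adverse events as percentages without intervals; zero serious events in 18 to 36 men would leave two-sided 95% upper limits of 18.5% to 9.7%

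*Combined protocol and SAP*

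**What the plan says.** Section 2.1.1 gives the primary objective as "To demonstrate the safety and feasibility of Psilocybin-Assisted Supportive-Expressive Group Psychotherapy (PA-SEGT) for demoralization in long-term AIDS survivors (LTAS", and the Abstract uses the same verb. The primary hypothesis in 1.4 says of the enrolled men that "they will experience no treatment-emergent serious adverse events".

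The primary analysis in 8.5 is that "Descriptive statistics (percentages) will be reported for the incidence of any Adverse Events reported, including suicidality as measured by the C-SSRS". Section 8.1 likewise plans descriptive and qualitative methods for safety. Neither section gives a confidence interval, an acceptable rate or a precision statement.

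On numbers, 8.2.1 "aims to enroll at least 18 subjects, and will have a maximum total sample size of 36". It then cites group-therapy practice, "so we plan to have at least 8 subjects complete the intervention". The Abstract gives the number of patients as "36 (maximum, with a minimum of 8".

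On the denominator, 8.4.1 and 8.5 put every enrolled patient in the safety analysis, whereas 5.2 calls each subject who receives psilocybin evaluable for safety.

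**The concern.** An objective to demonstrate safety and a hypothesis of no serious events are paired with a result that carries no measure of uncertainty. If no serious event occurs, the planned output is 0%. Nothing in the plan tells the reader how large a risk that figure leaves open.

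The plan is frank about its small sample elsewhere. Section 8.1 says that small-to-medium effects will probably go undetected. Section 8.5.1 concedes low power for the ANOVAs and adds Reliable Change Indices partly for that reason. Section 8.2.1 waives power calculations for efficacy only. Safety, the primary objective, gets no comparable caveat or remedy.

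The Abstract says that this trial will supply the first safety data for the intervention in this population. Whoever plans the next trial will start from these percentages.

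**Working it through.** **Inputs**
- Enrolment of 18 (target) and 36 (maximum): 8.2.1.
- Minimum of 8: completers in 3.2 and 8.2.1; patients in the Abstract.
- Attrition: "attrition rates of up to 45% reported in trials of other group therapies for existential distress in palliative care patients" (8.2.1).
- Psilocybin is given after four group visits: Table 5.1.
- Confidence level: none is stated. I assume 95% and show both conventions.
- True risks of 5% and 10%: illustrative assumptions.
- Men are treated as independent.

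**Step 1. The plan's own figure.** Eight completers with 45% attrition need 8 / (1 − 0.45) = 14.5, so 15 men. Rounded up to whole groups of six, this is 18. Accrual of 6 men every 6 months over 18 months also gives 18. Forward check: 18 × 0.55 = 9.9 completers, which exceeds 8. So 18 reproduces, but as a completer target. It does not come from any precision requirement for safety.

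**Step 2. What zero events would exclude.** With 0 events in n, the exact (Clopper-Pearson) upper limit is 1 − 0.025^(1/n) two-sided and 1 − 0.05^(1/n) one-sided. The chance of seeing no event at true risk p is (1 − p)^n.

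| n | Two-sided 95% limit | One-sided 95% limit | Chance of none, risk 10% | Chance of none, risk 5% |
|---|---|---|---|---|
| 36 | 9.7% | 8.0% | 2% | 16% |
| 18 | 18.5% | 15.3% | 15% | 40% |
| 10 | 30.8% | 25.9% | 35% | 60% |
| 8 | 36.9% | 31.2% | 43% | 66% |

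For n = 18: 1 − 0.025^(1/18) = 0.185, 0.9^18 = 0.150 and 0.95^18 = 0.397.

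**Step 3. Which rows apply.** Under 8.4.1 and the enrolment plan, the rows for 18 and 36 apply. The lower two rows apply only if the denominator is men who received psilocybin, as 5.2 can be read. Ten dosed is 18 × 0.55 = 9.9, assuming that all of the 45% attrition falls before dosing. Eight dosed uses the Abstract's minimum.

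**Step 4. Scale.** To exclude a 10% risk with zero events takes 36 men two-sided (29 one-sided). To exclude 5% takes 72 (59 one-sided).

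**The case against.** The best reply is that this is a Phase I pilot, openly descriptive, and that the hypothesis in 1.4 concerns the men in the trial and can be checked by counting. No section plans to infer a population risk or to declare a threshold met. Safety also does not rest on one percentage. Section 8.5 adds individual MoCA changes and CORF differences, 2.2.1 adds vital-sign thresholds and session ratings, 8.3 pauses enrolment after one severe, potentially related event, and 7.6 has monitor review after each group. Anyone can compute an exact interval from a reported count.

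Much of this stands. Descriptive reporting is normal here, and neither a test nor more men is needed. But an exact interval is itself descriptive. The pause and the monitor review act during conduct and do not say what the final percentage can support. The verb *demonstrate* remains in the primary objective.

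A reader might infer stronger versions of the point, and the documents do not support them:
- *That 36.9% is the general worst case, so one man in three could be at risk.* In 3.2 and 8.2.1, 8 is a minimum of completers, while the safety population is all enrolled with a target of at least 18. The figure needs the Abstract's 8 to be the safety denominator.
- *That zero events is the likely result even at a material risk.* With 18 men it has a 15% chance at 10% risk and 40% at 5%. It is more likely than not only below 1 − 0.5^(1/18) = 3.8%.
- *That a risk of one in five remains compatible with zero in 18.* 20% lies above the 18.5% limit, and 0.8^18 = 1.8%.
- *That shared groups necessarily widen the limits.* This needs positive within-group correlation in serious events. The documents give no value, and drug sessions are individual.

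**Conclusion.** The point holds as a mismatch between the claim and the analysis. On the population in 8.4.1, zero serious events would exclude risks above 18.5% with 18 men and above 9.7% with 36 (15.3% and 8.0% one-sided). That is useful information, but a bare 0% does not convey it and cannot by itself demonstrate safety. If only men dosed are counted, the limit could be 30.8% (10 dosed) or 36.9% (8 dosed), so the denominator has to be settled.

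The figures assume 95% confidence, independent men and no observed event. Section 9.7 refers to an appended Data and Safety Monitoring Plan that is not in the text I had, so the absence of an interval or criterion is judged on the protocol body. The point is worth acting on because the change is almost free and alters what the trial can say about its primary objective. It is not a flaw in the design or a reason to enlarge the study.

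**What to change.** - In 8.5, report serious events, adverse events by grade and C-SSRS positives as n/N with exact (Clopper-Pearson) 95% intervals.
- Name the denominator, and reconcile 5.2 (men receiving psilocybin) with 8.4.1 (all enrolled). If both are wanted, report both and say which is primary.
- In 2.1.1 and in the Abstract, change *demonstrate* to *estimate* or *describe* for safety.
- In 1.4 or 8.5, state what zero events would exclude at the achieved number, for example: *zero serious events in 18 men would exclude a risk above 18.5% (two-sided 95% exact limit)*.

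The cost is trivial analysis work and a less favourable safety statement. No extra men, visits or data are needed.

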Safety Assessments	Adverse events Vital signs  Adverse Event Medication Session Form  Columbia Suicide Severity Rating Scale  Community Observer Rating Form
Feasibility Assessments	Rate of Patient Recruitment Rate of Patient Retention (Sessions Attended and Follow-ups Completed) Client Satisfaction Scale Individual Patient and Important Other/Caregiver Interviews Supportive-Expressive Group Therapy Topic Grid Focus Groups with Patients and Important Others/Caregivers
Primary Outcomes	Demoralization Scale-II Inventory of Complicated Grief
Secondary Outcomes	Antiretroviral Medication Adherence Scale Alcohol Use Disorders Identification Test Center for Epidemiologic Studies Depression Scale—Revised Challenging Experience Questionnaire Clinical Global Impressions Scale Credibility/Expectancy Questionnaire Duke/UNC Functional Social Support Questionnaire—5 Drug Use Disorders Identification Test Experiences in Close Relationships scale—Modified 16 Group Psychotherapy Intervention Rating Scale Group Questionnaire HIV and Abuse Related Shame Inventory Individual Group Member Interpersonal Process Scale International Personality Item Pool—Openness to Experience-20 McGill Quality of Life Questionnaire—Revised-Short Multidimensional Assessment of Interoceptive Awareness—Revised Mystical Experience Questionnaire—30 Nature Relatedness Scale, Short Form Post-traumatic Growth Inventory—Short Form PTSD Checklist-5 Schedule of Attitudes towards Hastened Death Social Connectedness Scale-Revised

	State-Trait Anxiety Inventory Qualitative analysis of therapy sessions, interviews & focus groups
--	--

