### 2.2 Endpoints

#### 2.2.1 Primary Endpoints

- Safety will be defined based on the rate of adverse reactions (defined by the NIH Division of AIDS Table of Grading of Severity of Adult and Pediatric Adverse Events V2.0) (see Section 5 below). The safety of acute drug effects will be assessed by monitoring vital signs for tachycardia (HR>100bpm), bradycardia (HR<60bpm), hypertension (SBP>140mmHg or DBP>90mmHg) and hypotension (SBP<100mmHg or DBP<60mmHg). Drug-induced mental status changes will be assessed using the Adverse Event Medication Session Rating Form during drug sessions, pre and post measures with the Montreal Cognitive Assessment, and the Persisting Effects Questionnaire—Spirituality at study follow up. Suicidality will be assessed with the Columbia Suicide Severity Rating Scale. Follow-up safety data will be gathered for 3 months.
- Feasibility will partially be assessed in terms of the rates of patient recruitment and retention. Feedback on acceptability will also be gathered from subjects and caregivers/important others using the Client Satisfaction Scale. Patients and caregivers will also be invited to provide feedback during a focus group and patients will be invited to participate in individual interviews after the intervention. A SEGT Topic Grid will be used to evaluate video recordings of group therapy sessions in order to assess therapist adherence to the PA-SEGT model.

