### 6.2 Selection of Measures

Antiretroviral Medication Adherence Scale (AMAS)—A single item 11-point Likert scale (0%-100%) of ART medication adherence percentage over the past week. This scale was invented for this study.

Alcohol Use Disorders Identification Test (AUDIT) – A 10-item screening tool developed by the World Health Organization to assess alcohol consumption, drinking behaviors, and alcohol-related problems.

Center for Epidemiologic Studies Depression Scale-Revised (CES-D-R)—A 20-item validated 5-point Likert scale self-report scale for the detection of depression [155] that has been shown to be sensitive to change in symptoms in palliative care patients. [156].

Client Satisfaction Scale (CSS)—A 4-item 10-point Likert scale (“very dissatisfied” to “very satisfied”) designed for this study assessing satisfaction with the intervention.

Clinical Global Impressions scale (CGI)—A widely-used 3-item clinician-administered assessment developed by the NIMH to assess change in patients in psychopharmacology trials[157].

Challenging Experiences Questionnaire (ChEQ)—A validated 26-item 6-point Likert scale of the extent to which subjects experienced challenging experiences during a psychedelic drug treatment session[158]. The scale has 7 factors: fear, grief, physical distress, insanity, isolation, death and paranoia.

Columbia Suicide Severity Rating Scale (C-SSRS)—A validated 17-item scale that assesses suicidal ideation and behavior ([www.cssrs.columbia.edu](http://www.cssrs.columbia.edu)) according to the Columbia Classification Algorithm for Suicide Assessment (C-CASA), which the FDA Division of Psychiatric Products requires be used in clinical trials it oversees.

Community Observer Rating Form (CORF)—A 13-item 10-point Likert scale developed by Griffiths et al to triangulate behavioral observations of individuals administered psilocybin [17].

Concomitant Therapeutics Checklist (CTC)—A checklist designed for this study to assess the following categories of mental health therapies used over the last week: Prescription medications, non-prescription medications, psychotherapy, mutual aid groups, self-help

techniques, integrative medicine modalities, other.

Credibility/Expectancy Questionnaire (CrEQ)—A 6-item self-report measure of cognitive and affective assessments of a mental health therapy with high internal consistency and good test-retest reliability [159] that we have adapted for psychological distress.

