### 6.4.3.2 Baseline Caregiver/Important Other Assessments

- CORF

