### **6.4.5.2 Endpoint (Week 8) Study Measures for Caregivers/Important Others**

Patients' primary caregivers/important others will complete the CORF and CSS.

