### 6.4.6.3 3-Month Patients for Caregivers/Important Others

At 3 Months, primary caregivers/important others will be mailed a packet with the following measures: CORF and CSS. They will be called and encouraged to complete the packet.

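### The CORF is listed as a safety assessment, but section 8.5 summarises it only as a pre-to-post difference of means, with no per-man and no 3-month safety summary

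*Combined protocol and SAP*

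**What the plan says.** The abstract's row of safety assessments ends with the "Community Observer Rating Form". Section 6.2 describes it as "Community Observer Rating Form (CORF)—A 13-item 10-point Likert scale" and gives no scoring direction, no reliability and no size of change that would count as worsening.

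The form is collected three times. It is the only measure under 6.4.3.2 at baseline. At week 8, 6.4.5.2 says: "Patients' primary caregivers/important others will complete the CORF and CSS". At follow-up, 6.4.6.3 says: "At 3 Months, primary caregivers/important others will be mailed a packet with the following measures: CORF and CSS".

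Section 8.5 gives the CORF one sentence: "The differences of mean pre- and post-treatment scores on the CORF will be calculated". The next sentence treats the MoCA differently: "Differences in individual pre- and post-treatment MoCA scores will be assessed for each individual". Section 8.5 does not mention a 3-month CORF, although 2.2.1 states of safety in general: "Follow-up safety data will be gathered for 3 months".

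Elsewhere, 7.2 names the CORF as an example of an efficacy evaluation. Sections 8.1 and 8.5.1 describe changes in means out to 3 months in general terms, and 8.5.1 adds Reliable Change Indices. Neither names the CORF.

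**The concern.** A difference of means answers an efficacy question: did the group move? The safety question is whether any man got clearly worse. In a single-arm study of this size, harm seen by an observer would probably show in one or two men, and a mean sets their decline against the gains of the rest. Offsetting gains are what the study expects: the secondary hypotheses in 1.4 predict improvement in mean scores on a wide range of clinical measures, although the CORF is not among those named.

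Timing is the second gap. Observers rate the men at 3 months, inside the promised safety follow-up, but the section that reports safety stops at post-treatment. An observer-rated decline that appears after week 8 has no specified place in the safety results. Safety is part of the primary objective (2.1.1), so this matters more here than it would for an exploratory scale.

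**Working it through.** The plan states no CORF figure (no SD, threshold, alpha or power), so there is nothing of its own to reproduce. The check is how much improvement in the other men hides a given worsening.

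**Inputs from the documents**
- 8.2.1: at least 18 enrolled, at most 36, at least 8 completing, attrition of up to 45% in comparable trials. 18 × (1 − 0.45) = 9.9, so about 10 completers.
- 6.2: 13 items on a 10-point scale.

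**Assumptions, not in the documents**
- Higher scores are better.
- Clear worsening is D = 3 points per item (13 × 3 = 39 points on the total).
- Every man counted has an observer at both times.

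**Formula.** If k of n men worsen by D and the others each gain g, then

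mean change = [(n − k)g − kD] / n,

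which is zero when g = kD / (n − k).

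| n | Gain that cancels, one man worse | Gain that cancels, two men worse | Mean change, two worse and the others +0.5 |
|---|---|---|---|
| 8 | 3/7 = 0.43 | 6/6 = 1.00 | (3 − 6)/8 = −0.38 |
| 10 | 3/9 = 0.33 | 6/8 = 0.75 | (4 − 6)/10 = −0.20 |
| 18 | 3/17 = 0.18 | 6/16 = 0.38 | (8 − 6)/18 = +0.11 |
| 36 | 3/35 = 0.09 | 6/34 = 0.18 | (17 − 6)/36 = +0.31 |

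All values are points per item. With 18 men, two of them clearly worse and the rest half a point better, the planned summary reports an improvement of 0.11. A per-man listing of the same data reports 2/18 (11%) worse.

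**Range over D**, for 2 of 18 men: the cancelling gain is 4/16 = 0.25 if D = 2, 0.38 if D = 3, and 8/16 = 0.50 if D = 4.

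The effect depends on n. With 8 or 10 completers, two men worse and the others up by 0.5, the mean is negative and the worsening shows in its sign. With 18 or more it does not.

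**The case against.** Five points can be made on the other side.

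- **The CORF's safety status is thin.** It rests on one row of the abstract. Section 2.2.1 does not list the CORF, 7.2 treats it as efficacy, and in 8.5 its sentence follows the feasibility medians. For an efficacy measure a mean change is ordinary. This stands as a reason to keep the mean. It does not explain why a measure declared as safety has no safety summary.
- **A reader might infer that the 3-month CORF is never analysed.** The documents do not support that. Section 7.2 puts the CORF among efficacy evaluations, and 8.1 and 8.5.1 cover mean change to 3 months and Reliable Change Indices, an individual-level method. That cover is generic and exploratory, and a reliable change index needs a reliability that 6.2 does not give for the CORF.
- **A reader might infer that the CORF is the only information from outside observers.** It is not. Section 5.2 counts adverse events reported by primary caregivers as a safety parameter, 6.4.4.2 gives caregivers a clinician's pager number, and 6.4.6.1 and 6.4.6.4 invite them to focus groups and interviews. The CORF is the structured observer rating, not the sole route.
- **A reader might take the Appendix A schedule, which shows a CORF mark only at baseline, as contradicting 6.4.5.2 and 6.4.6.3.** That cannot be relied on. The CGI and AUDIT/DUDIT rows also lack marks that the text requires, so a missing mark cannot be told apart from damage to the table in the available copy.
- **The 8.5 sentence could mean each man's average over items.** The contrast with the MoCA sentence favours group means, but the ambiguity is itself a reason to reword.

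**Conclusion.** The point holds in a limited form. Section 8.5 specifies no individual-level and no 3-month CORF safety summary, and the difference of means it does specify can show no change, or improvement, when one or two men are clearly worse. For two of 18 men the cancelling gain is 0.38 points per item, or 0.25 to 0.50 as the assumed worsening runs from 2 to 4 points. With about 8 completers masking is weaker: one man's worsening is cancelled by a gain of 0.43, but two men's needs a full point.

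These figures rest on an assumed size of worsening and scoring direction, because the documents give neither. They illustrate the summary's behaviour and do not predict the result.

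A reader might go further and conclude that harm would be hidden in the trial's safety data as a whole. That does not follow. Adverse events, including those caregivers report, and C-SSRS suicidality are given as percentages, and MoCA change is assessed man by man. The weakness is confined to how the CORF is summarised. It is worth correcting because safety is a primary objective and the remedy costs very little.

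**What to change.** In section 8.5:

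- List each man's CORF change from baseline to week 8 and from baseline to 3 months, rated by the same observer where possible.
- State the scoring direction and define worsening before the data are seen. Counting any fall below baseline would label rating noise as harm.
- Report the number and percentage of men who worsened at each time, and the number with observer data at baseline, week 8 and 3 months. Section 8.5 does not say whether its two means are taken over the same men.
- Keep the difference of means as a secondary line.

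This goes further than the MoCA sentence, which promises individual assessment but no counts, percentages or threshold.

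The cost is a few sentences in the plan and one short listing in the report. The ratings are already collected, so there is no added burden on participants or caregivers. The downside is a little more descriptive reporting and some false signals from rating noise, which the pre-specified definition limits but does not remove.
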